9.3.4.1 UPCR

Percent change from baseline in UPCR at Week 13 was chosen as the primary endpoint because proteinuria is a characteristic feature of FSGS and 1 of its main prognostic factors. Urine samples will be collected for UPCR using the first morning void, which is standardly used in clinical practice to determine accurate urine protein levels. As UPCR is variable within an individual, 3 samples will be taken during screening, Week 9, and Week 13; and the average of the 3 values will be used to determine baseline, Week 9, and end-of-treatment UPCR values.

9.3.4.2 SF-36

Change in SF-36 from baseline over the study treatment period will be assessed as an exploratory outcome. SF-36 is a patient-reported generic measure of health status. It has been

previously used to evaluate health-related quality of life in patients with chronic kidney disease, including FSGS.^{22,23}

9.3.5 Use of Telemedicine for Study Visits

Telemedicine may be used for a number of study visits as detailed in Table 3-2 and Table 3-3. These visits will include home health nurse visits to the subject's home to complete assessments. All visits must have a consultation between the subject and investigator (i.e., in person, phone, or telemedicine video conference) within 1 business day after the home health visit, in order to check-in and collect AEs. Subjects and investigators may choose to conduct individual visits in the clinic or through use of home health. Periodic phone or telemedicine video visits may also be done to allow the investigator and subject to communicate directly; these visits may be done face-to-face in the clinic at the discretion of the investigator.

If local regulations or site practice do not allow telemedicine, all visits will be conducted at the site.

9.3.6 Eligibility Review

An independent, external expert with appropriate clinical and scientific background will evaluate the histopathological eligibility criteria to ensure that the subjects meet the study's definition of FSGS. Details of the process will be included in a separate procedure manual.

9.4 Prior and Concomitant Medications

Information about all prior and concomitant medications, including the subject's FSGS medications, other medications, and herbal and naturopathic remedies administered from 28 days before the Screening Visit through the SFUV, if applicable, will be recorded in each subject's source documents. For subjects who are screened but not subsequently randomized, details of prior medication will only be documented in the subjects' source documents.

Subjects in Cohort 1 and Cohort 2 who are taking ACE inhibitors, ARB, neprilysin inhibitor, sodium-glucose co-transporter-2 inhibitor, or a renin inhibitor must remain on a stable medication regimen at least 28 days before the Screening Visit through the Week 13 or ETT (if applicable) Visit. Subjects in Cohort 2 who are taking systemic corticosteroids must remain on a stable low dose (i.e., ≤ 10 mg/day of prednisone or prednisone equivalent) from at least 28 days before the Screening Visit through the Week 13 or ETT (if applicable) Visit. During the Off-Treatment Period, every effort should be made to avoid starting, stopping, or modifying doses of these medications. If it becomes clinically necessary to alter a subject's antihypertensive regimen during the study, changes to an antihypertensive medication dose or addition of a new antihypertensive medication are recommended before changes are made to any ACE inhibitor, ARB, neprilysin inhibitor, or renin inhibitor.

9.5 Study Restrictions

Study restrictions are summarized in Table 9-1. A nonexhaustive list of medications is provided in the Study Reference Manual.

Table 9-1 Study Restrictions

Restricted	Timing of Restriction		
Medication/Food/Activity ^a	Start	Stop	
Moderate and strong CYP3A4 inhibitors or inducers, including consumption of herbal medications (e.g., St. John's Wort)	None allowed within 14 days before the first dose of the study drug	Completion of Safety Follow-up Visit assessments	
Systemic corticosteroids (applicable to Cohort 1 only)	None allowed within 4 weeks before the first dose of the study drug	Completion of the last study assessment	
Immunosuppressants	None allowed within 12 weeks before the first dose of study drug	Completion of the last study assessment	
Rituximab	None allowed within 6 months before the first dose of study drug	Completion of the last study assessment	
Other investigational drugs or devices	28 days before first dose of study drug, 5 half-lives before first dose of study drug dose, or time determined by local requirements (whichever is longer)	Completion of the last study assessment	
Creatine or creatine-containing dietary supplements	7 days before first dose of study drug	Completion of Safety Follow-up Visit assessments	
Grapefruit, grapefruit juice, pomelos, orange marmalade, Seville/blood oranges	7 days before first dose of study drug	Until last PK sample is taken	

^a See Section 9.4 for guidance on concomitant medications.

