Standard 12-lead ECG		X		Complete after SF-36 and before other assessments after subject has been supine for at least 5 minutes. ECGs (Section 11.6.4), vital signs, and blood draws should be performed in said order.
Vital signs		X		Complete before other assessments listed below after subject has been at rest for at least 5 minutes; they should be seated during the assessment (Section 11.6.3). Blood pressure will be collected in triplicate.

^a The postdose PK sampling visit is required for all subjects, with the exception of those who complete an ETT Visit.

The SFUV and Part B Week 4 Off-treatment Follow-up Visit may occur on the same day, provided the visit windows are met for both visits.

Visit windows for Part B are as follows: Week 4 Visit (Day 120 ± 2 weeks), Week 8 Visit (Day 148 ± 2 weeks), Week 12 Visit (Day 176 ± 2 weeks).

Table 3-3 Study VX19-147-101: Postdose PK Sampling, Safety Follow-up Visit, and Part B Off-treatment Follow-up Period

On-treatment Follow-up reriou					
Event/Assessment	Postdose PK Sampling (Approximately 48 hours after the last dose of study drug) ^a	SFUV 28 (± 7) Days After Last Dose of Study Drug ^b	Part B: Optional Off-treatment Follow-up Visits (Part B Week 4 ^b , 8, and 12)	Comments	
Weight		X		Weight will be measured with shoes off and light weight closing (no outerwear). (Section 11.1).	
Abbreviated physical examination		X		In addition to the scheduled visits, symptom-directed physical examinations will occur at any time during the study if triggered by AEs or if deemed necessary by the investigator (Section 11.6.3).	
Serum chemistry		X Fasted		A blood sample will be collected following an overnight fast (Section 11.6.2).	
Hematology		X		A blood sample will be collected (Section 11.6.2)	
Coagulation		X		A blood sample will be collected (Section 11.6.2)	
VX-147 PK Sampling	X			A blood sample will be collected (Section 11.2.1).	
Urine sample		X	X	The first morning urine void will be collected and used for efficacy, safety, and biomarker analyses (Sections 11.3 and 11.6.2). Refer to sample handling guidelines to ensure samples are collected and submitted appropriately for analysis.	
β-hCG (urine)		X		All female subjects of childbearing potential (Section 11.6.2). This can be collected in the same sample as the other urine sample.	
Adverse events		gning of ICF through UV	NA	Section 11.6.1	

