9 STUDY IMPLEMENTATION

9.1 Study Design

This is a single-arm, open-label, 2-part study. In Part A, all subjects will receive VX-147 at a dosage of 15 mg qd for 2 weeks and VX-147 at a dosage of 45 mg qd for 11 weeks. Part A will be enrolled in 2 cohorts: Cohort 1 and an optional Cohort 2. Cohort 1 includes up to 10 subjects

with UPCR approximately \geq 3 g/g and < 10 g/g and eGFR approximately \geq 30 mL/min/1.73 m². Optional Cohort 2 includes approximately 10 subjects with UPCR approximately \geq 0.8 g/g and <2.7 g/g and eGFR approximately \geq 30 mL/min/1.73 m².

[figure not shown]
Subjects in Cohort 1 and Cohort 2 are permitted to take a stable low dose of systemic corticosteroid (prednisone ≤ 10 mg per day or prednisone equivalent) and/or an allowed immunosuppressant (i.e., tacrolimus, mycophenolate, or cyclosporine).

Enrollment of Cohort 1 and Cohort 2 will be managed through the interactive web response system (IWRS).

In Optional Part B, subjects will be followed for up to 12 weeks for evaluation of proteinuria off-treatment (Section 9.1.3).

All subjects will complete a SFUV at 28 (\pm 7) days after the last dose of study drug.

Figure 9-1 VX19-147-101 Study Design

D: Day; PK: pharmacokinetics; qd: once daily; UPCR: urine protein to creatinine ratio; W: Week Notes: The figure is not drawn to scale. After completing Part A, subjects will be followed monthly for up to 12 weeks or until UPCR returns to baseline, whichever occurs first. All subjects will be required to complete a SFUV at 28 (± 7) days after the last dose of study drug.

Proteinuria will be assessed at multiple timepoints throughout the Treatment Period and Off-treatment Follow-up. Triangles represent timepoints for the primary analysis.

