9.1.3 Part B

Participation in Part B is optional. After the last Part A Visit, subjects will be followed off-treatment at a visit scheduled every 4 weeks (\pm 2 weeks) to assess the change in proteinuria after stopping administration of VX-147 (Table 3-3). Part B visits will continue until the UPCR level reaches \geq 90% of baseline levels or 3 months after the last dose of study drug, whichever occurs first. If a subject has not achieved \geq 90% of baseline UPCR by the Part B Week 12 Visit, the Part B Week 12 Visit will be the last study visit.

Subjects will not be allowed to participate in Part B if (1) their UPCR level during Part A remained \geq 90% of baseline or (2) their UPCR level reached \geq 90% of baseline before the Part A Week 13 Visit and remained at that level through the Week 13 Visit.

The SFUV and Part B Week 4 Off-treatment Follow-up Visit may occur on the same day, provided the visit windows for both visits are met.

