9.5 Study Restrictions

Study restrictions are summarized in Table 9-1. A nonexhaustive list of medications is provided in the Study Reference Manual.

Table 9-1 Study Restrictions

Restricted	Timing of Restriction			
Medication/Food/Activity ^a	Start	Stop		
Moderate and strong CYP3A4 inhibitors or inducers, including consumption of herbal medications (e.g., St. John's Wort)	None allowed within 14 days before the first dose of the study drug	Completion of Safety Follow-up Visit assessments		
Nonpermitted Immunosuppressants Note: This includes all immunosuppressants except tacrolimus, mycophenolate, and cyclosporine, which are permitted.	None allowed within 12 weeks before the first dose of study drug	Completion of the last study assessment		
Rituximab	None allowed within 6 months before the first dose of study drug	Completion of the last study assessment		
Other investigational drugs or devices	28 days before first dose of study drug, 5 half-lives before first dose of study drug dose, or time determined by local requirements (whichever is longer)	Completion of the last study assessment		
Creatine or creatine-containing dietary supplements	7 days before first dose of study drug	Completion of Safety Follow-up Visit assessments		
Grapefruit, grapefruit juice, pomelos, orange marmalade, Seville/blood oranges	7 days before first dose of study drug	Until last PK sample is taken		

^a See Section 9.4 for guidance on concomitant medications.

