9.3.2.2 Analyses of Exploratory Efficacy Variable

Percent change from baseline in UPCR over time during the Treatment Period: Analysis of this variable will be based on steps as described for primary analyses in Section 9.3.1.2. Subjects non-compliant with study drug will not be included in the analysis. The GMPC from baseline in UPCR, GSE (%) along with the corresponding 2-sided 80% CI and 95% CI at each post-baseline visit (Week 1, Day 15, Week 3, Week 5, Week 9, and Week 13) will be provided. The GMPC from baseline in UPCR at each post-baseline visit during the Treatment Period will also be presented in a figure.

Percent change from baseline in urine albumin-to-creatinine ratio (UACR) at Week 13: Analysis of this variable will be conducted in the same way as described for primary analyses Section 9.3.1.2. Subjects non-compliant with study drug will not be included in the analysis. The GMPC from baseline in UACR at Week 13, GSE (%) along with the corresponding 2-sided 80% CI will be provided.

Percent change from baseline in UACR over time during the Treatment Period: Analysis of this variable will be based on steps as described for primary analyses in Section 9.3.1.2. Subjects non-compliant with study drug will not be included in the analysis. The GMPC from baseline in UACR, GSE (%) along with the corresponding 2-sided 80% CI at each post-baseline visit (Week 1, Day 15, Week 3, Week 5, Week 9, and Week 13) will be provided. The GMPC from baseline in UACR at each post-baseline visit during the Treatment Period will also be presented in a figure.

Percent change from baseline in UPCR at the end of the Off-treatment Follow-up Period: Analysis of this variable will be based on steps as described for primary analyses in Section 9.3.1.2. Subjects non-compliant with study drug will not be included in the analysis. The GMPC from baseline in UPCR, GSE (%) along with the corresponding 2-sided 80% CI and 95% CI at each visit in Off-treatment Follow-up Period (Part B Week 4, Week 8, and Week 12) will be provided. The GMPC from baseline in UPCR at each post-baseline visit during the Off-treatment Period will also be presented in a figure.

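### The creatine restriction ends at the Safety Follow-up Visit, before the Part B Week 8 and Week 12 UPCR samples (minor; exploratory endpoint only)

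*Protocol*

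**What the plan says.** Protocol Section 9.5, Table 9-1, bars "Creatine or creatine-containing dietary supplements" from "7 days before first dose of study drug" until "Completion of Safety Follow-up Visit assessments". Versions 2.0 and 6.0 carry the same row. In the same table, the rows for immunosuppressants that are not permitted, rituximab and other investigational products run to "Completion of the last study assessment".

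On timing, Section 9.1 states: "All subjects will be required to complete a SFUV at 28 (± 7) days after the last dose of study drug". Table 3-3 places the later Part B visits at "Week 8 Visit (Day 148 ± 2 weeks), Week 12 Visit (Day 176 ± 2 weeks", after a Week 4 visit at Day 120 with the same tolerance. Section 9.1.3 gives the purpose of these visits as "to assess the change in proteinuria after stopping administration of VX-147". It continues them until UPCR is at least 90% of baseline or three months have passed since the last dose.

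Section 11.3 (Version 6.0) calculates UPCR from protein and creatinine measured in urine. SAP Section 9.3.2.2 reports the geometric mean percent change (GMPC) in UPCR with its confidence intervals "at each visit in Off-treatment Follow-up Period (Part B Week 4, Week 8, and Week 12) will be provided".

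**The concern.** The restriction stops at the visit where serum creatinine is last scheduled, not where UPCR is last measured. From the SFUV onwards a Part B volunteer may take creatine freely. If that raises urine creatinine, the denominator of UPCR grows and the ratio falls with no change in protein excretion. Part B exists to show what proteinuria does once the drug is withdrawn, so a falsely low value would look like a persisting effect.

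Nothing else in the documents closes the gap:

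- Section 9.4 asks sites to avoid changes during Part B only for the medicines it lists, and creatine is not among them.
- Version 6.0 extends medication recording through Part B, but recording is not a restriction. The text names medications and herbal or naturopathic remedies, not dietary supplements.
- Under SAP Sections 9.1 and 9.2.4, something started after the SFUV counts as post-treatment and is only listed.
- The Part B analysis in SAP Section 9.3.2.2 leaves out subjects not compliant with study drug, not voids taken on creatine.

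**Working it through.** **The plan's own precision figure.** Protocol Section 12.1 assumes a log-scale SD of 0.672 and n = 10. The 80% half-width is t(0.90, 9 df) × SD/√n = 1.383 × 0.672/√10 = 0.294, which matches the stated 0.294. It serves below only as a yardstick.

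**Timing.** The last dose is the day before the Week 13 visit (Table 3-2), whose window is Day 90 to 92, so the last dose falls on Day 89 to 91. The SFUV at +21 to +35 days falls on Day 110 (89 + 21) to Day 126 (91 + 35), nominally Day 119 (91 + 28).

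| Part B visit | Window (days) | Nominal gap after SFUV | Range of gap |
|---|---|---|---|
| Week 4 | 106 to 134 | 120 − 119 = 1 day | may precede or coincide; at most 134 − 110 = 24 days |
| Week 8 | 134 to 162 | 148 − 119 = 29 days | 134 − 126 = 8 to 162 − 110 = 52 days |
| Week 12 | 162 to 190 | 176 − 119 = 57 days | 162 − 126 = 36 to 190 − 110 = 80 days |

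Weeks 8 and 12 therefore always fall in the unrestricted interval. If the three-month limit in Section 9.1.3 is taken as 91 days, the maximum is 91 − 21 = 70 days.

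**Size for one subject.** Let x be the fractional rise in urine creatinine. Neither the existence nor the size of this rise is stated in the documents, so x is an assumption. With a creatine-free baseline, measured UPCR = true UPCR/(1 + x):

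- x = 10%: 1/1.10 = 0.909, so 9% low
- x = 25%: 1/1.25 = 0.800, so 20% low
- x = 50%: 1/1.50 = 0.667, so 33% low

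A subject truly at 100% of baseline reads below 90% when 1/(1 + x) < 0.90, that is, when x > 1/0.90 − 1 = 11.1%.

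**Size for the group.** With k users among 10 subjects, the mean log change moves by −k × ln(1 + x)/10. The number of users is also an assumption. At x = 25%:

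- k = 1: −0.223/10 = −0.022, a factor of exp(−0.022), or −2.2%
- k = 3: −0.067, or −6.5%

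Against the half-width of 0.294 these are about 8% (0.022/0.294) and 23% (0.067/0.294).

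**Dependence on the baseline.** Table 3-1 allows the three baseline voids from Day −28 and requires the third by Day −5. The restriction starts seven days before dosing. Three voids on separate days are all covered only if they fall on Days −7, −6 and −5. A subject on creatine at screening has a baseline of true/(1 + x). If that subject resumes after the SFUV, the factor (1 + x) appears in both values and cancels. If the subject stays off creatine in Part B, the bias reverses. At x = 25% the baseline reads 0.80 of true, and the 90% line sits at 0.90 × 0.80 = 0.72 of true.

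**The case against.** The best case for the current text is that the stop date has a coherent reading. Serum creatinine feeds the eGFR and acute kidney injury assessments and is last scheduled at the SFUV, so the row may have been written to protect serum values. No passage is contradicted. That stands as an explanation of the date. It does not protect the UPCR samples that follow.

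Three stronger inferences are tempting, and the documents do not support them.

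- *The bias always favours the drug.* This needs a creatine-free baseline, which a restriction starting seven days before dosing does not secure. A user at screening who resumes is compared like with like. Moving only the stop date could make matters worse for such a subject: at +25%, someone with a genuine 28% residual reduction would reach the 90% line and leave Part B.
- *A full return of proteinuria would be lost from the results.* No endpoint or SAP output classes subjects as returned or not returned. The 90% rule only decides whether another visit takes place, and Week 12 is the last visit regardless. A subject who reads low attends more visits, not fewer.
- *The unprotected period is eleven weeks.* That is the extreme of the windows (80 days); the nominal figure to Week 12 is 57 days.

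It is also fair to say that Version 6.0 medication recording and the SAP listing of post-treatment medications may make creatine use visible, provided sites record supplements there.

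**Conclusion.** The gap is real in the current protocol. The creatine row stops at the SFUV, and two of the three Part B UPCR visits always come after it. For a subject with a creatine-free baseline who takes creatine in that interval, UPCR can read low by 9% to 33% over the assumed range, and a rise in urine creatinine above 11.1% is enough to cross the exit line. For a subject already on creatine at screening the bias largely cancels or can reverse.

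The reach is limited. The stop date bears on one exploratory endpoint of an optional study part and on the rule for ending its visits. It cannot affect the Week 13 measurement, which precedes the SFUV. On illustrative counts of one to three users in ten, the group shift is small beside the planned precision. The conclusion rests on creatine raising urine creatinine and on some volunteers using it; the documents quantify neither. This is a minor point, worth correcting because the correction is cheap.

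**What to change.** In the creatine row of Table 9-1, replace the stop with "Completion of the last study assessment", wording the table already uses. Change the start of the same row so that it covers the screening UPCR voids that form the baseline. Both ends should move together, so that baseline and Part B values are comparable. The unrestricted interval during Part B then falls from 57 days nominal to zero; sample size and precision are unchanged.

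If it is too late to amend, use the Part B medication review in Version 6.0 (Table 3-3 and Section 9.4), confirm that it captures dietary supplements, flag Part B voids taken on creatine, and repeat the Part B GMPC without them.

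The cost is one table row. Part B volunteers avoid a supplement for roughly 8 to 11 more weeks (57 to 80 days), and all subjects for somewhat longer before dosing: 28 − 7 = 21 extra days if the first void is on Day −28. No visits, samples or staff are added.

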9.6 Administration

VX-147 will be administered as 15 mg tablets, orally, as shown in Table 3-2.

Study drug will be administered according to the following guidelines:

- The first dose in each period must be administered under the supervision of site medical staff or a home health nurse. Subjects will be monitored for 4 hours after receiving the first dose of each Treatment Period
- On days of scheduled visits, the dose of study drug will be administered after predose assessments have been completed.
- Study drug will be taken at approximately the same time on each dosing occasion. For example, subjects that administer VX-147 dose at 8AM on Day 1 should administer all subsequent doses at $08:00AM \pm 2$ hours.
- Study drug may be taken with or without food.

- Subjects will swallow the study drug whole, with a full glass of water and will not chew it before swallowing.
- On days of intensive PK sampling, the date, dose taken, and time of study drug administration will be recorded for the 2 doses before PK sample collection and on the morning of PK sample collection.
- Subjects will be instructed to bring all used and unused materials associated with the study drug to the site or the nurse will take these materials at each study visit; study drug will be dispensed at each visit, as appropriate.

Missed Doses

If a subject misses a dose and recalls the missed dose within 6 hours, the subject should take his/her dose according to the guidance above. If more than 6 hours have elapsed after his/her usual dosing time, the subject should skip that dose and resume his/her normal schedule for the following dose. An example is provided below:

• If the morning dose of study drug should have been taken at approximately 08:00AM, and the subject remembers at 12:00PM that he/she forgot to take his/her dose, he/she should take the dose as soon as possible. If they remember after 2:00PM that they forgot to take the morning dose, they should skip that dose and resume the normal schedule the next day.

Additional information is provided in the Pharmacy Manual.

